
In addition, there is still limited evidence about the effects of upright walk-training on risk markers of CVD in individuals with chronic SCI. Furthermore, previous studies have not investigated the effects of walk-training on risk markers of CVD in individuals with motor complete SCI. The influence of walk-training on

the pro-inflammatory markers has also not been studied in both incomplete and complete SCI. To explore those issues would further extend our knowledge to better understand the benefits of walking exercise in individuals with chronic SCI.

II. Research Plan and Design

A. Study Objectives:

The **primary objectives** are 1) to examine the feasibility of an 8-week walk-training program and 2) to examine the potential association between changes in resting and exercise heart rate and changes in four major factors after 8-week walk-training in individuals with chronic SCI. The **secondary objective** is to collect pilot data before and after the 8-week walking exercise for evaluating changes in risk markers of CVD in study participants.

B. Study Type and Design:

The proposed study is a pilot, single group, pre- and post-clinical study design for gathering feasibility and preliminary data for preparing a subsequent future clinical trial. At the initial contact with a study candidate, a phone screening will be conducted by a member of our research team to determine whether an individual is qualifying for the study. An eligible participant will receive BWSTT with assistive training device three sessions a week for eight weeks (a total of 24 sessions). Outcome measures will be taken at baseline and after completion of the walk-training program.

C. Sample size, statistical methods, and power calculation

In this pilot study, we focus more on feasibility issues. We will analyze the data of the study to find trends and to gather pilot data for preparing a future trial. Thus, we will recruit a total of 19 participants.

We have calculated sample size for one factor based on specific aim#2. With power of 80% and significance level of 0.1, we need 15 participants to find a significant correlation of ($r = 0.6$) between the one factor and the outcome variable. Considering drop out of 20 %, we will recruit a total of 19 participants.

D. Subject Criteria (See Vulnerable Populations appendix, if applicable):

a. *Inclusion criteria:*

We will include spinal injured individuals between 18 and 60 years old, who have paraplegia (T1-L2) SCI, and who are scored less than 5 in Functional Independence Measure, Locomotion: Walk. The onset of SCI must be one year or more at the beginning of the study. Participants must not be participating in any other similar gait training activities. Participants must have medical approval from their physician to participate in walk-training. We will encourage women and all minority group to participate in this study. Children will be not included in the study because we are recruiting individuals who are 18 or older.

b. *Exclusion criteria:*

We will exclude individuals who have one of following conditions:

- 1) Major Cardiovascular diseases
- 2) Other neurological diseases
- 3) Muscle spasticity (greater than 3 according to Ashworth scale)
- 4) Severe orthopedic issues such as joint stiffness and fractures
- 5) Osteoporosis (bone mineral density T-score less than -2.5)[155]
- 6) Inflammatory diseases or infections
- 7) Open wound and pressure ulcer

- 8) Pregnant women
- 9) Cognitive or psychiatric disorders
- 10) Uncontrolled autonomic dysreflexia; sudden increase in blood pressure

Participants who take anti-spasticity medications will not be excluded from the study as long as they meet eligibility criteria for the study. They will be instructed to maintain the same medications and dosage throughout the study period.

c. *Withdrawal/Termination criteria:*

- 1) Insufficient compliance with exercise program, 2) Withdrawal of consent form for any reason, 3) Physician discretion, and 4) Death.

d. We will not recruit a participant who is participating in other research studies.

E. Specific methods and techniques used throughout the study

E.1. outcome measures:

Aim#1: To examine feasibility (recruitment, perception, compliance, retention, and walking performance) of an 8-week (3 sessions per week, 30 min per session) walk-training program in patients with chronic SCI.

Throughout the study, we will collect data on feasibility measures of recruitment, perception, compliance, retention and walking performance. The recruitment rate will be assessed by recording number of participants who are screened for eligibility, those who are excluded because of eligibility criteria, and those who decline to participate in the study. Information on perception will be acquired through a questionnaire that will be administered to participants at the end of walk-training program. The questionnaire, which is derived from previous studies, will evaluate participant’s acceptance of and satisfaction with the walk-training program (*Appendix I*) [156-159]. Data on compliance rate will be documented during a period of training. The total number of completed sessions and incomplete sessions along with reasons for absence will be recorded throughout the study. Data on retention will be obtained by recording the number of participants who drop out during the study along with their reasons. Data on walking performance will be obtained by recording walking time, treadmill walking speed, and number of stepping during each session.

Aim#2: To examine correlations between changes in four factors (muscle activity, autonomic function, spasticity, and lung capacity) and changes in heart rate after the walk-training program in individuals with chronic SCI.

The outcome measures listed below will be performed at baseline (pre-measurement) and within 72 hours after completing the 8-week walk-training (post-measurement). Participants will be instructed to restrain from caffeine and cigarette smoking, physical activity for at least 12 hours before testing and will be asked to empty their bladder (or urine bag) prior to the measurements.

The resting heart rate will be measured during sitting position after 5 minutes rest. Exercise heart rate will be measured during a graded treadmill walking test with the same testing conditions (i.e., treadmill speed and body weight support) pre- and post-training as described in past studies [160-162]. Participants will walk on a treadmill with starting warm-up speed of 0.5 miles/hour. The treadmill speed will be increased by 0.2 miles/hour every two minutes. The heart rate will be monitored by a polar sport T31 transmitter (Polar Electro Inc., New York) and will be recorded at the beginning and every two minutes. Leg assistance will be provided to participants as needed (*Figure 2*).

Figure 2: Measure of HR response during a graded treadmill walking test

Electromyography (EMG) system will be utilized to measure the activity of four muscles in the lower limbs: biceps femoris, rectus femoris, gastrocnemius medialis, and tibialis anterior. Prior to the test, surface electrodes will be placed on these muscles bilaterally according to the SENIAM guidelines [163]. The EMG recording will be obtained during walking on a treadmill. At least 10 steps cycle will be recorded. Foot switches will be placed on participant's insoles, and it will detect the time each foot was on the ground. The level of BWS (50%) and treadmill speed (0.9 miles/hour) will be kept constant for each participant during the measurement at baseline and after completing the study, as described in a previous study [127]. The average root-mean-square EMG for each muscle during gait cycle will be calculated and summarized.

Cardiac autonomic function will be determined through power spectral of HRV using electrocardiography system. As described in previous studies [137, 141], HRV will be recorded in a sitting position after at least 5 min rest. Data acquisition will last 10 min and will be performed in a room with temperature between 20 and 22 C, with no noise atmosphere. During the recording, participants will be asked to breathe normally and remain silent, without speaking or moving. Recording of HRV will be performed around the same time and conditions pre- and post-measurement. HRV frequency domain, including total power, LF and HF powers, and ratio of LF/HF, will be calculated and analyzed using a computer program made in matlab.

A previous study reported consistent muscle spasticity in individuals with paraplegia during the day and from day to day [164]. However, to control for fluctuation in muscle spasticity during the day and the time of day, conducting the assessment will be consistent for each participant during pre- and post-testing [165]. In addition, the assessment will be performed by the same therapist in order to minimize interrater variability of examiners [166]. Muscle spasticity for the lower extremities (hip, knee and ankle flexors and extensors) will be assessed through Modified Tardieu Scale (MTS). MTS is a reliable clinical assessment for measuring muscle tone and joint angle reaction in response to passive stretch at specified velocities (as slow as possible (V1), falling under gravity (V2) or as fast as possible (V3)) [167]. The patients will be tested in the supine position, and the quality of muscle reaction and angle of muscle reaction of the lower limbs will be assessed at specified speeds (V1, V2, V3). The level of muscle reaction is measured on a 6-point scale (0 indicated "No resistance throughout passive movement" and 5 indicates "Joint immobile"). The angle at which the muscle reaction occurs will be determined via a goniometer. The angle of the full range of motion during slow passive movement is defined as R2, while the angle of muscle reaction during fast passive movement is defined R1. The difference between R2 and R1 (R2-R1) represents the dynamic tone component of the muscle spasticity. The large spasticity angle indicates the more spastic muscle (*Appendix II*).

Vital lung capacity will be measured through a spirometer (Spirotek® Spirometer, MIR USA INC.) The procedures for measuring vital capacity will be conducted according to the guidelines from the American Thoracic Society/European Respiratory Society [168]. Participants will sit upright on a chair with back and arm support. First, participants will be instructed how to perform the test. Then, nose clips will be placed on participant's nose, and participant's lips will be sealed around the mouthpiece of the spirometer to prevent air leakage. To perform the test, a participant will be informed to breathe normally three times, and then they will be instructed to maximally inhale and exhale. The participant will be instructed to fill and empty their lung during inspiration and expiration, respectively. In addition, the participant will be instructed to not flex or extend his/her neck or trunk during the test. Three readings will be obtained, and the largest reading will be recorded. There will be 30 second rest between each reading.

Aim#3: To investigate the effect of an 8-week walk-training program on lipid profile, the level of glycated hemoglobin (HbA1c), and the level of pro-inflammatory markers in individuals with chronic SCI.

Blood samples will be collected by a registered nurse or a certified technician at the KU Hospital and then will be transferred to the Diabetes Research Laboratory at the KUMC for analysis. We will collect blood samples from each participant at baseline and within 72 hours after completing training.

Blood samples will be collected in the morning (between 8 and 11 am) from each participant after 12-hour overnight fasting; i.e., no eating, drinking (except water), or smoking 12 hours prior to measurement. About 20 ml of blood samples will be collected from an antecubital vein into a tube containing heparin as an anticoagulant. Immediately after drawing, the blood sample will be centrifuged at 1,800 g for 10 min at room temperature. Subsequently, serum will be separated from the blood cells, and then serum specimens will be transferred to plastic tubes which will be stored at -80°C until analysis. We will assess serum concentrations of TC, LDL-C and HDL-C using an enzymatic colorimetric assay (abcam, Cambridge, MA, USA; catalog no. ab65390; Crystal Chem, USA, catalog no 80069). We will analyze HDL-C after separating HDL-C from LDL-C and very low-density lipoprotein by precipitation with magnesium chloride in aqueous dextran sulfate 500. For inflammatory markers, Serum concentrations of CRP (abcam, Cambridge, MA; catalog no ab108826) and IL-6 (abcam, Cambridge, MA; catalog no ab46042) will be determined using an enzyme-linked immunosorbent assay (ELISA) according to the manufacturers' protocols.

According to American Diabetes Association and World Health Organization recommendation, HbA1C has been used as a tool to diagnose diabetes because it reflects the average glucose levels over the life of the red blood cell (around 2 to 3 months).[169] We will collect a small drop of blood (5 microliters) from the middle finger of the right hand. Immediately, blood samples will be placed on a blood fingerstick and then analyzed using a device A1CNow+ System (Test Medical Symptoms at Home, Inc., Maria Stein, OH, USA). Studies showed that A1CNow+ System test is strongly correlated with reference methods using venous blood sample test [170]

Exploratory aims: To investigate effects of an 8-week walk-training program on lower limbs muscles strength and spasticity, functional independence, the level of depression, anxiety and stress, and health-related quality of life (HRQOL) in individuals with chronic SCI.

Muscle strength will be evaluated using lower extremity motor score (LEMS), according to guidelines of ASIA [3]. LEMS is a manual muscle testing that assesses the strength of five key muscle groups of the lower extremities bilaterally: the hip flexors, knee extensors, ankle dorsiflexors, great toe extensors, and ankle plantarflexors. Each muscle group will be graded from 0 (absence of muscle contraction) to 5 (active movement with the full range of motion against full resistance). The total score of LEMS ranges from 0 to 50 (*Appendix III*).

As mentioned previously, muscle spasticity for each participant will be assessed at about the same time of day during pre- and post-testing in order to control for fluctuation in muscle spasticity during the day [165]. In addition, the assessment will be performed by the same therapist during pre- and post-testing in order to minimize variability between examiners [166]. Muscle spasticity will be assessed through Modified Ashworth Scale (MAS) and Penn Spasm Frequency Scale. MAS is a subjective scale for clinical assessment of involuntary resistance to passive movement and, hence, muscle tone [165, 167]. An examiner will move the patient's limb through its full range of movement and will rate the amount of resistance felt. Resistance is rated based on a 6-point scale (grades 0, 1, 1+, 2, 3, 4), with lower scores indicating no spasticity and higher scores representing increasing resistance to passive movement. The MAS will be used to assess passive movements of the ankle and knee flexors and extensors (*Appendix IV*). The Penn Spasm Frequency Scale is a two components self-report questionnaire that assesses an individual's perception of spasticity frequency and severity [171]. The first component is a 5-point scale assessing the frequency with which spasms occur ranging from "0 = No spasms" to "4 = Spontaneous spasms occurring more than ten times per hour. The second component is a 3-point scale assessing the severity of spasms ranging from "1 = Mild" to "3 = Severe". If an individual indicates that he/she has no spasms in the first component, the second component is not evaluated (*Appendix V*).

In addition, we will quantitatively measure spasticity of the knee joint (quadriceps and hamstring muscle) of the right leg using an isokinetic dynamometer (Biodex Medical System, Inc., Shirley, New York), as

described in the previous protocols with some modifications [172-175]. A participant will be seated on a dynamometer chair with back tilted 85° and hip joint positioned at 90°. The trunk and legs will be stabilized by using straps across the chest, waist, and upper thigh. The axis of the dynamometer will be aligned with the lateral femoral condyle of the knee joint. The distal attachment of the lower limb to the lever of dynamometer will be made approximately 3 cm above the lateral malleolus and will be secured with the distal of the leg by straps. In the beginning, the knee joint will be positioned at 85° of knee flexion and then will be passively moved five times at low velocity of 5 degrees/second from 85° knee flexion to 25° knee flexion and back to 85° knee flexion. Following that, one set of five continuous passive movements from 85° of knee flexion to 25° of knee flexion will be performed at different velocity 15, 30, 60, 90, 120 degrees/second with return velocity of 5 degrees/second to assess knee flexors spasticity. One set of five continuous passive movements from 25° of knee flexion to 85° of knee flexion will be performed at different velocity 15, 30, 60, 90, 120 degrees/second with return velocity of 5 degrees/second to assess knee extensors spasticity. The order of velocity of movement will be randomized. There will be 60 seconds rest break between each movement velocity.

The Spinal Cord Independence Measure (SCIM) self-report version (SCIM-SR) will be utilized to evaluate the level of functional independence. The SCIM-SR is a valid self-reported questionnaire that is designed to measure functional ability of daily activities for persons with SCI.[176] It has an excellent agreement with the clinician administered SCIM version-III.[176] This questionnaire contains 17 items, divided into three subscales: self-care (items 1-4), respiration and sphincter management (items 5-8), and mobility ability (items 9-17). The total score of SCM-SR ranges from 0 to 100, which indicates the level of functional independence. The higher score represents higher level of functional independence (*Appendix VI*).

The level of depression, anxiety, and stress will be measured using Depression Anxiety Stress Scales-21 (DASS-21).[177] DASS-21 is a self-administered questionnaire that is designed to assess the negative emotional states of depression, anxiety, and stress over the past few weeks. It consists of three subscales with seven items in each subscale (total of 21 items). The response to each item is given on a 4-point Likert scale ranging from 0 = “Did not apply to me at all” to 3 = “Applied to me very much or most of the time”. The score for each subscale is calculated by summing the scores for the relevant items. The low score indicates normal level, whereas the high score indicates extremely severe level of depression, anxiety, and stress (*Appendix VII*).

Change in HRQOL will be assessed via the Short form-36 (SF-36). SF-36 is a self-reported, 36-items questionnaire that assesses eight domains of perceived HRQOL during the previous 4 weeks.[178, 179] The eight domains include physical functioning, role-physical functioning, bodily pain, general health, vitality, social functioning, role-emotional functioning, and mental health. The higher score represents better HRQOL (*Appendix VIII*).

E.2. Intervention protocol

We will perform gait training at Neuromuscular Research Laboratory in the Department of Physical Therapy and Rehabilitation Science at the KUMC. Participants will receive three sessions a week of BWSTT with assistive training device for 8 weeks; total of 24 sessions. The duration of each training session will last 30 minutes (three bouts of ten-minute walk-training). Previous studies showed that 6 to 8 weeks (three times a week) of walk-training could have positive impacts on the cardiovascular and pulmonary system in individuals with SCI [97, 100-102]. During walk-training, the participant will wear a harness which is attached to an overhead motorized lift to provide body-weight support (BWS) and to prevent the risk of falling (*Figure 3*). At the initial sessions, 60% of participant’s body weight will be supported. Later, BWS will be decreased by 5% at each session as tolerated without knee buckling. However, if the participant is not able to tolerate new BWS or shows knee buckling, BWS will be increased by 5%. This training protocol has been used and described in past studies.[114, 180, 181] In addition, two thigh braces which are attached

[figure not shown]
to a pulley system via pulling cords will be attached onto participant's thigh and will be secured using straps (Figure 1). Two therapists will operate the training device to assist the participants with hip and knee flexion and ankle dorsiflexion of the legs during the swing phase of a gait cycle. Another therapist will stand behind the participant and will help with balancing and supporting the participant if it is needed. The participant will be encouraged to actively move the legs throughout training. At the beginning of training, initial treadmill speed will be set at 0.5 miles/hour. The participant will walk at 0.5 miles/hour for three to four minutes to warm up. Subsequently, the treadmill speed will be gradually increased by 0.2 miles/hour every two minutes until participant's heart rate reaches 40-50% of his/her heart rate reserve (maximal heart rate – rest heart rate) as recommended by American College of Sports Medicine guidelines.[65] Maximal heart rate will be determined using age-predicted maximal heart rate (220 – participant's age).[182] The participant will be allowed to take three to five minutes rest after 10 minutes of training. Participants can request rest at any time when needed. In the last three minutes, participants will walk at low speed (0.5 miles/hour) for cooling down. To ensure the safety of training, heart rate and blood pressure will be monitored throughout training. Participant's heart rate should not exceed 85% of age-predicted maximal heart rate, and participant's blood pressure should be maintained below 220/110 mm Hg.

E.3. Study plan and Timeline:

After a participant signed a consent form and agreed to participate in the study, pre-training measurements will be taken. Then, the participant will receive walk-training three times per week for eight weeks. After completing intervention, participants will be given one day as a break to wash out immediate effects of the intervention, and then the participant will be scheduled for collecting post-training measurements within 72 hours (Figure 4).

Figure 3: Body weight supported treadmill

Figures 4: Study plans

The timeline of this project will be one year (Table 1). First, we will begin recruiting and enrolling participants after the study is approved by Institutional Review Board (Human Subjects Committee) at the KUMC. Our goal is to enroll at least three participants a month in the study. We expect that we will meet our enrollment goal within 7 months of the study timeline. At 9 months, we expect that we will finish with providing training to participants. Second, we will analyze the blood sample and clinical assessments at 10 and 11 months. Finally, we will conduct statistical analysis at 12 months.

Table 1: Study timeline

Project activities	One-year timeline											
	1	2	3	4	5	6	7	8	9	10	11	12
Enrollment	█	█	█	█	█	█	█					
Intervention	█	█	█	█	█	█	█	█	█			
Outcome measures analysis										█	█	
statistical analysis												█

F. Risk/benefit assessment:

1. Physical risk:

During laboratory testing, participants might feel minor pain at the needle site, when blood sample is drawn from his/her body. Pain sensation will go away after blood drawing. Participants might feel muscles fatigue and sore, sweating, and physical discomfort during or after exercise. Also, there are possibility that participants may experience abnormal blood pressure response, fainting, irregular, fast, or slow heart rate during walking exercise, and in rare case, heart attack, stroke, or death. Throughout exercise session, we will carefully monitor participants to reduce the risk associated with walking exercise. We will immediately stop exercise if we observed any sign of risks on participants. Our research teams are trained to do CPR when it is need. Walk-training will be performed at moderate-intensity which has minimal risk and is convenient for individuals with SCI. Participants will get medical clearness from their physicians in order to participate in the study.

2. Psychological risk: N/A

3. Social risk: N/A

4. Economic risk: N/A

5. Potential benefit of participating in the study:

Participants may or may not benefit from participating in this study. Our research team hope that information gathered in this study will contribute to scientific knowledge of the benefit of walking exercise on cardiovascular health in individuals with SCI

G. Location where study will be performed:

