B.2. Cardiovascular Disease in SCI Population

With advances in medical care, the life expectancy of people with SCI has increased significantly as compared to past few decades [10]. However, cardiovascular disease (CVD) is the common leading cause of death among people with SCI and occurs at the early age in people with SCI as compared to able-bodied people [11]. The findings are consistent in demonstrating a high prevalence of CVD among people with SCI [5, 12]. It has been estimated that the prevalence rate of symptomatic CVD in SCI population (30-50%) is higher compared to able-bodied population (5-10%) [3]. SCI population has 2.72 times higher risk of heart disease and 3.72 times higher risk of stroke compared to the general population [13]. In term of mortality

from CVD, a cohort study that followed individuals with SCI for five years after discharge from inpatient rehabilitation found that 37% individuals died due to cardiovascular causes [14].

B.3. Risk Factors of CVD in SCI population

Physical inactivity is a major risk factor for the development of CVD in general population [15, 16]. Likewise, lack of physical activity and/or prolonged sitting in people with SCI is associated with increased risk of CVD [17]. Previous studies reported low levels of dynamic physical activity among individuals with chronic SCI, and around 50 % of them did not meet recommended levels of physical activity for people with disabilities [18, 19]. Physical inactivity contributes to increase in multiple risk factors of CVD including reduced cardiovascular fitness, abnormal lipid profile, diabetes mellitus, and elevated levels of pro-inflammatory markers [17, 20, 21]. It is well known that reduced cardiovascular fitness is associated with increased risk of CVD [22], and those risk factors, such as abnormal lipid profile, diabetes mellitus, elevated levels of pro-inflammatory markers, play important roles in damaging endothelium of blood vessels and formation of atherosclerosis, leading to developments of ischemic heart disease, stroke, and peripheral vascular disease [23-25]. A previous study found that approximately 76.9 % of SCI population had two or more risk factors for CVD [26].

Elevated heart rate:

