Regular exercise is necessary to reduce or prevent secondary complications following SCI, including cardiovascular events and cardio-metabolic syndrome. According to the Canadian physical activity guidelines for adults with SCI, individuals with SCI should engage in at least 20 minutes of moderate to vigorous intensity aerobic exercises twice a week and in strength training exercises twice a week[64]. Similarly, American College of Sports Medicine recommends people with SCI to participate in moderate to vigorous intensity aerobic exercises two to three times per week from 20 to 30 minutes [65]. For cardio-metabolic health benefits, a recent guideline suggested that adults with SCI should engage in 30 minutes moderate to vigorous intensity aerobic exercises three time per weeks [66]. A variety of modalities such as arm cycling, functional electrical stimulation (FES) leg cycling, circuit resistance training, and walk-training have been utilized to improve cardiovascular health in SCI population [67]

Upper Extremity Exercises

Upper limbs exercise has been shown to improve cardiovascular fitness and reduce risk markers of CVD in patients after SCI. A previous study reported a decrease in submaximal exercise heart rate in individuals with cervical SCI after 8 weeks of low-intensity arm ergometer training [68]. When comparing the effect of different intensities of arm cycling in individuals with chronic SCI, moderate-intensity training significantly reduced submaximal exercise heart rate compared to baseline, and it also significantly increased HDL-C and decreased triglyceride (TG), LDL-C, and the TC/HDL-C ratio as compared to low-intensity training [69]. A similar study found that high-intensity arm cycling significantly decreased TG and TC/HDL-C ratio and improved insulin sensitivity in individuals with SCI as compared to low-intensity arm cycling [70]. In a randomized control study, 6-week hand-bike exercise program three times weekly in persons with complete SCI significantly reduced the fasting levels of insulin and insulin resistance and increased the levels of HDL-C compared to the control group [71]. Similar findings were reported in other studies with 12-week or 3-

month of arm cycling exercise [72, 73]. Positive changes in levels of inflammatory markers including CRP and IL-6, were also reported after 8-12 weeks of arm cycling in individuals with chronic SCI [74, 75].

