FES-leg cycling, and resistance training have been utilized to exercise paralyzed muscles below the level of lesion and to activate large muscle mass in order to increase the level of physical activity and prevent cardiovascular complications after SCI. Some of past studies have shown that FES-leg cycling, or resistance training helped to improve cardiovascular fitness (i.e. heart rate adaptation) and reduced the risk makers of CVD following SCI [80-84]. Faghri et al.[80] examined the effects of 12-week FES-leg cycling on cardiopulmonary response at rest and submaximal exercise test in individuals with incomplete and complete SCI. They found that resting heart rate slightly decreased in individuals with paraplegia and significantly increased in individuals with quadriplegia following training, and submaximal exercise heart rate significantly decreased in both groups. In regard to changes in risk markers of CVD, 8-10 weeks of FES-leg cycling exercise significantly decreased levels of glucose and insulin [83, 85] and levels of pro-inflammatory markers, including CRP and IL-6. [85]. A number of studies have explored physiological mechanisms of improvements in glucose homeostasis following lower extremities exercise. Past studies showed that 8 weeks of FES-leg cycling significantly increased levels of GLUT-1 and GLUT-4, insulin-stimulated glucose transport, and insulin-mediated disposal in individuals with complete SCI [86, 87].

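### Other exercise may start, stop or change between baseline and post-test without being prevented or recorded, so the uncontrolled pre-post comparison could not separate its effect from that of walking

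*Protocol*

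**What the plan says.** Four rules in the protocol bear on what participants do besides the training.

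- Section II.D.a (inclusion criteria): "Participants must not be participating in any other similar gait training activities".
- Section II.D.d: "We will not recruit a participant who is participating in other research studies".
- Section II.D.b, on those taking anti-spasticity drugs: "They will be instructed to maintain the same medications and dosage throughout the study period".
- Section II.E.1, on test days: "Participants will be instructed to restrain from caffeine and cigarette smoking, physical activity for at least 12 hours before testing".

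On design, section II.B states: "The proposed study is a pilot, single group, pre- and post-clinical study design". Section V.A analyses Aim 3 and the exploratory aims by paired t-tests at the 0.05 level, and Aim 2 by regressing heart-rate change on change in each factor. No term for other exercise appears in either.

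The background in section I.B.4 describes what other exercise has done in this population. On arm cycling: "Positive changes in levels of inflammatory markers including CRP and IL-6, were also reported after 8-12 weeks of arm cycling". On 12 weeks of FES-leg cycling: "submaximal exercise heart rate significantly decreased in both groups". The same section also reports studies of arm and FES exercise with no change in lipids, heart rate or other risk markers.

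**The concern.** None of the four rules reaches an exercise programme followed at a clinic, gym or home. The gait-training criterion is limited by its subject, the research bar by its setting, the stability instruction to one class of drug, and the activity restriction to 12 hours. A participant may therefore begin, drop or change arm-cycling, FES-cycling or resistance work during the eight weeks, and the data would not show it.

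The secondary hypothesis attributes change from baseline to the walking programme. With no control group, any other cause of change between the two tests is absorbed into that estimate. Starting another programme could look like a benefit of walking; giving one up to make room for three visits a week could hide a real benefit. For Aim 2, arm work that lowers heart rate without altering leg EMG would add noise to the correlation that the primary hypothesis concerns. What was never recorded cannot be adjusted for later, whatever the analysis plan says.

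**Working it through.** **1. The plan's own figure.** Section II.C gives 15 evaluable participants for r = 0.6, significance level 0.1 and power 80%, and 19 recruited after 20% dropout. The Fisher approximation with a two-sided test is n = ((1.645 + 0.842) / atanh(0.6))² + 3 = (2.487 / 0.693)² + 3 = 15.87. Simulated power of the exact two-sided test at n = 15 is 80.6%, so 15 is right. For dropout, 15 / 0.8 = 18.75, rounded up to 19. The sample size reproduces, and this point does not depend on it. It supplies n = 15 for what follows.

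**2. Do the background studies concern this trial's outcomes?**

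| Outcome here | Reported to change (I.B.4) | Reported not to change (I.B.4) |
|---|---|---|
| Exercise heart rate (Aim 2) | 8 weeks of arm ergometry, in cervical injury; 12 weeks of FES-leg cycling | 19 weeks of FES-leg cycling |
| HDL-C (Aim 3) | 6 weeks of hand-biking | low- or high-intensity arm cycling; FES-leg cycling |
| CRP, IL-6 (Aim 3) | 8-12 weeks of arm cycling; 8-10 weeks of FES-leg cycling | some 10- or 16-week upper-limb studies found no benefit on risk markers generally |

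Glucose and insulin also fell after FES-leg cycling, but the glycaemic outcome here is HbA1c. The evidence makes an effect plausible, not established.

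**3. Paired tests.** The following inputs are assumptions, not protocol figures: n = 15 completers, no true walking effect, k participants who start other exercise, and a shift of d standard deviations of the change score in each of them. The expected mean shift is k × d / 15. Rejection rates come from simulating the two-sided 5% paired t-test.

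| Starters k | Mean shift, d = 0.5 to 1.0 | Rejection rate |
|---|---|---|
| 1 | 0.03 to 0.07 SD | about 5% |
| 2 | 0.07 to 0.13 SD | 5.3% to about 6.3% |
| 4 | 0.13 to 0.27 SD | 6.9% to 12.1% |
| 6 | 0.20 to 0.40 SD | 10.1% to 22.7% |

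If m participants stop and shift the other way, the mean shift is (k − m) × d / 15. With four starting and two stopping, rejection is about 4.6% (d = 0.5) and 3.8% (d = 1.0); with three and three, about 4.1% and 2.2%. Opposing shifts widen the spread while largely cancelling in the mean. This holds for near-balanced mixes only: five starting and one stopping gives (5 − 1) × d / 15, the same mean shift as four starters.

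**4. Aim 2.** Suppose the true correlation is 0.6 and other exercise lowers heart rate by 0.5 to 1.0 SD in two to six of the 15 without altering EMG. Power falls from about 81% to between 70% and 79%. If instead there is no true association and other exercise moves both EMG and heart rate (FES work might), the nominal 10% test rejects in 10.3% to 10.8% of studies at d = 0.5 and in 12.4% to 18.6% at d = 1.0, again for two to six participants.

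**The case against.** The protocol itself calls the evidence on arm and FES exercise inconsistent, and some of the positive results fit poorly: one heart-rate result is in cervical injury, whereas this trial enrols T1-L2, and another followed 12 weeks of training. This stands. It limits how large an effect may be assumed, but a factor of uncertain effect is still worth holding constant when doing so is cheap.

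A reader might infer from "around 50 % of them did not meet recommended levels of physical activity" (section I.B.3) that the other half exercise regularly and that exposure is therefore widespread. The document does not support that step. The same passage describes activity as low, a stable habit does not bias a within-person change, and no section gives a rate of starting or stopping.

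A reader might also infer that the analysis would credit other exercise to walking as a matter of course, or that the primary hypothesis is undermined. Neither follows. Appreciable inflation needs about four or more of 15 participants to change in the same direction while also attending three sessions a week; with one or two it is slight, and near-balanced mixes make the test conservative. Aim 1 is untouched, and Aim 2 is diluted only modestly.

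Finally, the study is a declared single-group pilot, so some loss of attribution is accepted by design, and a sensitivity analysis is ordinarily left to an analysis plan. Both are fair. But the instruction and the data collection belong in the protocol, and no analysis plan can supply them afterwards.

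**Conclusion.** The gap is real and limited. Other exercise outside research may change between baseline and post-test, is not recorded, and could bias the Aim 3 and exploratory paired tests in either direction; it could modestly dilute the Aim 2 correlation. How far cannot be known from the protocol. The illustrative rejection rates run from below the nominal 5%, when starters and stoppers roughly offset, through about 5-6% with one or two starters, to 10-23% with six. They rest on assumed numbers of changers and assumed shifts of 0.5 to 1.0 SD, with 15 completers and no walking effect. Severity is minor to moderate for a feasibility pilot: the data are meant to prepare a later trial, and the omission cannot be repaired once they are collected.

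**What to change.** Beside the medication instruction in section II.D.b, add that participants are to keep any other structured aerobic, FES or resistance exercise unchanged from baseline until post-testing. In section II.E.1, add one question on other exercise (type, frequency, any change) at each test visit. Repeat the Aim 2 and Aim 3 analyses without participants who report a change; this can be stated in section V.A or left to the analysis plan.

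The cost is one sentence, one question per visit, slight participant burden, and a smaller n in the sensitivity analysis, which should be read as descriptive. A required period of stable exercise before baseline is optional and not part of the core fix: it would delay some candidates, and enrolment is planned to finish within 7 months with about one in four of those screened expected to join.
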